2.3.2 Secondary endpoint(s)
The evaluation of clinical equivalence of BVE compared to ABPI in the determination of presence or absence of significant PAD will be carried out by means of the estimation of overall accuracy
$Overall\ accuracy\ calculation = \frac{TN + TP}{TN + TP + FN + FP} = \frac{Number\ of\ correct\ assessments}{Number\ of\ total\ assessments}$
Where TN = True Negative, TP = True Positive, FN = False Negative and FP = False Positive.
The secondary endpoint is met when it is shown that BVE is equivalent to the existing measurements (ABPI) in the determination of presence or absence of significant PAD (binomial outcome).
equivalence will be confirmed if the difference between $PS_2$ and $PT_2$ is lower than the margin of equivalence $D_2$ .
$Ha_2$ : $PS_2 - PT_2 < D_2$
2.4 Sample Size Calculations

a maximum of 188 subjects will be enrolled in the clinical investigation in
2.8 Study/ Trial Success
It will be considered a trial success when:

All subjects are successfully recruited

All required limbs are measured

 
All values are adequately collected and considered valid
 
At least the primary endpoint is met.
 

2.9 Subgroups of Analysis
The clinical equivalence of BVE testing performed by staff specifically trained on BVE (no vascular
technologists/specialists) will be compared to BVE testing performed by vascular technologists/
specialists.
In addition, the clinical equivalence of BVE testing performed on subjects with a medical history of diabetes, smoking activity or hypertension, will be compared to BVE testing performed on healthy subjects.

2.11	

3.0 DESCRIPTIVE ENDPOINTS AND ADDITIONAL DATA
3.2 Adverse Events
All the AEs, SAEs, adverse device effects (ADEs), serious adverse device effects (SADEs), unanticipated adverse device effects (UADEs), and unanticipated serious adverse device effects (USADEs) will be summarized for all subjects enrolled in this clinical investigation in terms of the number of events, number of subjects with events, the percentage of subjects with events and event rate (number of events per patient per month).

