Document ref: CIP summary from BVE-01- v2.0

Date: 14Feb2022

CIP SUMMARY

| Clinical Investigation code | BVE-01 |
|---|--|
| Title | Clinical Evaluation of the BlueDop Vascular Expert for Assessing Peripheral Arterial Disease |
| Objectives | Primary objective: Evaluate the clinical equivalence (assessment of accuracy) of BVE as binary result (either presence or absence of significant peripheral arterial disease) compared to arterial duplex ultrasound in a group of patients referred for evaluation of PAD of the lower limbs when performed by a vascular specialist. |
| | Secondary objectives: Evaluate the clinical equivalence (assessment of accuracy) of BVE as binary result (either presence or absence of significant peripheral arterial disease) compared to ABPI in a group of patients referred for evaluation of PAD of the lower limbs when performed by a vascular specialist. Assess the safety of the BVE device. |
| | Exploratory objectives: Evaluation of the BVE System for clinical performance including time needed to perform BVE, inter-operator variability and number of BVE non-diagnostic tests. |
| Device Under Investigation | Bluedop Vascular Expert (BVE) Model: Medical BVE100 Set 1: Tablet s/n 1001+ Charger s/n 1001 + Egg s/n 1002 |
| Number of Subjects Required for Inclusion in Clinical Investigation | 188 limbs required (188 subjects max., but enrolled number of subjects may be lower if, for certain subjects, both limbs are included in the study). |
| Clinical Investigation Design | Prospective, multi -center, nonrandomized, open label, single arm study |
| Primary Endpoint | Evaluation of clinical equivalence of BVE compared to Arterial duplex in the determination of presence or absence of significant PAD |
| Major Secondary Endpoints | Evaluation of clinical equivalence of BVE compared to ABPI in the determination of presence or absence of significant PAD. Evaluation of BVE safety |
| Subject Follow-up | N/A – No follow-up visits are planned in the study. |
| Inclusion Criteria | Subject must provide written informed consent prior to any clinical investigation related procedure. At least 18 years of age. Referred for duplex ultrasound of the lower limb (s) with suspected or previous history of peripheral arterial disease Must have an ABPI performed as part of the assessment |

Confidential Page 1 of 2

Document ref: CIP summary from BVE-01- v2.0

Date: 14Feb2022

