| | 5. Able to obtain a brachial cuff blood pressure reading6. Must have a valid ankle duplex ultrasound measurement at the Posterior Tibial Artery (PTA) and Dorsalis Pedis Artery (DPA) |
|--------------------|---|
| Exclusion Criteria | 1. Subject is currently participating in another clinical investigation or has participated in another clinical investigation in the past 30 days prior to the start of the present study; |
| | 2. Pregnant or nursing subjects and those who plan pregnancy during the clinical investigation follow-up period |
| | 3. Presence of other anatomic or comorbid conditions, or other medical, social, or psychological conditions that, in the investigator's opinion, could limit the subject's ability to participate in the clinical investigation or to comply with follow-up requirements, or impact the scientific soundness. |
| | Inability of refusal to give informed consent. |
| | Lower extremity would or compromised skin of the legs that prevents access to the studied arteries. |

Confidential Page 2 of 2

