#### 2.0 ANALYSIS CONSIDERATIONS

2 4	۸na	lveic	Donu	lations
2.1	Ana	IVSIS	Popu	lations

ziiii ziiioiiiioiii populatioii (ziii /	2.1.1	Enrollment	population (	(EnP)
---	-------	------------	--------------	-------

Enrollment population (EnP) includes those subjects with at least one lower limb referred for evaluat	ion
of PAD.	

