#### 2.1.2 Eligible population (EIP)

Eligible population (EIP) comprises the subset of enrolled patients who have at least one valid determination of PAD with both devices (BVE and arterial duplex).

•

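### Device-effect percentages are planned over all enrolled subjects, who need not have had a BVE test, so they may understate risk per exposed subject

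*SAP*

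**What the plan says.** SAP 3.2 (Adverse Events) covers AEs, SAEs and four classes of device effect (ADE, SADE, UADE, USADE) in a single rule: they "will be summarized for all subjects enrolled in this clinical investigation in terms of the number of events", the number of subjects affected, "the percentage of subjects with events and event rate (number of events per patient per month". One denominator, all enrolled subjects, therefore serves every category.

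SAP 2.1.1 says that the enrollment population "includes those subjects with at least one lower limb referred" for PAD evaluation. It does not mention a BVE test.

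SAP 2.1.2 defines the only other population visible in the text. The eligible population "comprises the subset of enrolled patients who have at least one valid determination of PAD with both devices", meaning BVE and duplex.

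The inclusion criteria in the CIP summary depend on other tests. They include "Must have an ABPI performed as part of the assessment", an obtainable brachial cuff pressure, and "Must have a valid ankle duplex ultrasound measurement at the Posterior Tibial Artery (PTA) and Dorsalis Pedis Artery (DPA". None of them refers to BVE.

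SAP 1.4.2 makes the safety of BVE an endpoint, judged by AEs and SAEs. The CIP summary also plans to study "inter-operator variability and number of BVE non-diagnostic tests", so BVE tests that fail to give a result are expected and will be counted.

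**The concern.** A device-effect percentage is normally read as the risk to a person on whom the device was used. Here the denominator is enrolment, and enrolment as written does not depend on the device having been used. An enrolled subject who never has BVE cannot contribute a device effect but adds one to the denominator. Such subjects can therefore only lower the device-effect percentage. With no events at all, they make the upper confidence bound look tighter than the exposed data support.

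The one narrower visible population is not a remedy. The eligible population requires a valid BVE result, so it drops subjects in whom BVE was started but was non-diagnostic. Those subjects were exposed and belong in a safety denominator.

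**Working it through.** **Is there a figure in the plan to reproduce?** No. The documents give no adverse-event rate and no number of enrolled subjects without a BVE test. The only relevant number is the maximum of 188 subjects (CIP summary; SAP 2.4), used below as an illustrative N. Its derivation is not visible and this point does not depend on it. If fewer subjects are enrolled because both limbs are included, the ratio between the two percentages is the same for a given untested share.

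**Can an untested subject enter the denominator?** Setting the sections side by side:

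- SAP 3.2 uses all enrolled subjects.
- SAP 2.1.1 makes referral of a limb the defining property of the enrolled. The inclusion criteria add conditions on ABPI, cuff pressure and duplex, but none on BVE.
- SAP 2.1.2 treats a valid result on both devices as a property of a subset of the enrolled. Enrolment and valid testing are therefore distinct in the SAP itself. This does not show that anyone goes without a BVE attempt, because a started but non-diagnostic test also falls outside the subset.

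The rule as written therefore allows untested subjects in the denominator. It does not say that there will be any.

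**Size.** Let N be the number enrolled, u the share never tested with BVE, and x the number of subjects with a device effect, all of them necessarily exposed.

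- Reported percentage: R = x / N
- Exposed-subject percentage: E = x / [N(1 − u)]
- Hence R = E × (1 − u)
- With zero events, the one-sided 95% upper bound on n subjects is 1 − 0.05^(1/n)

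The values of u and x are assumptions. With N = 188 and the untested number rounded to whole subjects:

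| Assumed u | Untested | Exposed | x = 5: reported / exposed | x = 10: reported / exposed | Zero events: bound on 188 / on exposed |
|---|---|---|---|---|---|
| 0% | 0 | 188 | 2.66% / 2.66% | 5.32% / 5.32% | 1.58% / 1.58% |
| 1% | 2 | 186 | 2.66% / 2.69% | 5.32% / 5.38% | 1.58% / 1.60% |
| 2% | 4 | 184 | 2.66% / 2.72% | 5.32% / 5.43% | 1.58% / 1.61% |
| 5% | 9 | 179 | 2.66% / 2.79% | 5.32% / 5.59% | 1.58% / 1.66% |
| 10% | 19 | 169 | 2.66% / 2.96% | 5.32% / 5.92% | 1.58% / 1.76% |
| 20% | 38 | 150 | 2.66% / 3.33% | 5.32% / 6.67% | 1.58% / 1.98% |

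For example, at u = 10%, 5/188 = 2.66% and 5/169 = 2.96%, a difference of 0.30 percentage points. At u = 5% the difference is 0.13 points.

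**What is not affected.** Event counts and numbers of subjects with events do not change. The relation R = E × (1 − u) applies to device effects only. An untested subject can have an all-cause AE, so the direction for AEs and SAEs is not fixed.

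**The case against.** A reader might infer that the published percentages will include unexposed people and will be diluted. The documents do not support that, for these reasons:

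- No section says that any enrolled subject goes without BVE. The study is single arm, and SAP 2.8 makes complete measurement of the required limbs a condition of success.
- SAP 1.3 describes the study population as people who satisfy the entry criteria. ABPI and duplex results could be known before enrolment. BVE could also come first, in which case a subject who later failed another test would have been exposed.
- The order of tests and the operational point of enrolment are not given in the public CIP summary.
- SAP 3.2 does not cite the population in 2.1.1 by name. Equating the two is natural but not stated.
- Parts of the SAP are not visible, and its abbreviation list includes ITT and per-protocol populations that the visible text does not use. A safety set could be defined in unseen text.

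It can also be said that section 3.0 is descriptive, that no safety threshold is visible, and that a reader told how many subjects were tested could recompute the percentages.

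Most of this stands, and it is why the point is conditional and modest. It does not remove the point. The single-arm design and the success condition express intent; neither takes an untested enrolled subject out of the SAP 3.2 denominator. The table of contents lists only the enrolled and eligible populations under 2.1, and the visible sentence in 3.2 assigns the summary to all enrolled subjects. Recomputation by the reader works only if the number tested is reported, and the visible text does not promise that.

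**Conclusion.** The point holds as a conditional one. As written, the device-effect percentages may include subjects never tested with BVE. They may then understate risk per exposed subject by a factor of 1 minus the untested share. That share is unknown and could be zero, in which case the two percentages are the same. Under assumed shares of 5% and 10%, with 5 affected among 188, the report would show 2.66% in place of 2.79% and 2.96%. This rests on reading enrolment in SAP 3.2 as SAP 2.1.1 defines it, and on there being no exposed-subject safety set in text that is not public.

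Two stronger readings should be left aside. Dilution is possible but not shown. Nor do the documents establish a need to count exposure by limb and operator: both limbs may be included, but repeat testing of the same subject is not stated.

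This is a cheap improvement to the safety summary and not a flaw that puts the trial's conclusions in doubt.

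**What to change.** In SAP 3.2:

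1. Report ADE, SADE, UADE and USADE percentages over all subjects in whom a BVE test was started on at least one limb, whether or not the result was valid. Do not use the eligible population for this.
2. State how many enrolled subjects had no BVE attempt.
3. Keep the all-enrolled AE and SAE summary beside it.

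The cost is one definition and one extra denominator. Sites need to record BVE attempts in any case in order to count non-diagnostic tests. The downside is that device-effect percentages may become slightly less favourable. If every enrolled subject is tested, nothing changes.

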#### 1.4.2 Primary safety endpoint

To characterize and confirm the safety of BVE, safety will be evaluated by assessing the AEs and SAEs.

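### Does the adverse-event rate per patient per month in SAP 3.2 need redefining or replacing in a study with no planned follow-up visits?

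*SAP*

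**What the plan says.** SAP 3.2 summarises all classes of adverse event and device effect, for every enrolled subject, in four ways. Three are counts or proportions: "the number of events, number of subjects with events, the percentage of subjects with events". The fourth is the "event rate (number of events per patient per month". SAP 1.4.2 describes the safety evaluation only in general terms: "safety will be evaluated by assessing the AEs and SAEs".

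On follow-up, the Subject Follow-up row of the CIP summary reads N/A and adds that "No follow-up visits are planned in the study". Exclusion criterion 2 in the same summary nevertheless covers "those who plan pregnancy during the clinical investigation follow-up period", and criterion 3 covers conditions that could limit the ability to participate "or to comply with follow-up requirements".

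SAP 2.8 lists the conditions for trial success. The only one that concerns a result is "At least the primary endpoint is met". SAP 2.3.1, headed as the primary endpoint, is the comparison of BVE with arterial duplex.

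**The concern.** A rate per patient per month is defined only once patient-months are defined. If observation ends with the test visit, patient-months are close to zero and the rate depends on the time booked per subject. If the same fixed window applies to everyone, the rate is events per subject divided by a constant. Two analysts working from the public SAP could therefore report very different rates from the same data. A reader might then compare the result with monthly rates from studies that do follow patients.

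The CIP summary adds to the doubt by giving follow-up as not applicable while two exclusion criteria presuppose it. Safety carries the label of a primary safety endpoint in SAP 1.4.2, and SAP 3.2 is the only visible text on how events will be summarised. An undefined quantity there deserves a check.

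**Working it through.** The plan states no figure for this rate, so there is nothing to reproduce. The check asks how far the rate can move, what else moves with it, and whether any conclusion depends on it.

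**Inputs.** The maximum of 188 subjects comes from the CIP summary and SAP 2.4. The lower figure of 94 is 188/2, the case where every subject contributes both limbs; the CIP summary says the "enrolled number of subjects may be lower if, for certain subjects, both limbs are included in the study". One event in total and the observation windows are assumptions. A month is taken as 30.4375 days (730.5 hours).

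**Formula.** Patient-months = subjects × days / 30.4375. Rate = events / patient-months.

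| Assumed window per subject | Patient-months, 188 subjects | Rate, 1 event | Patient-months, 94 subjects | Rate, 1 event |
|---|---|---|---|---|
| 1 hour | 0.257 | 3.89 | 0.129 | 7.77 |
| 1 day | 6.18 | 0.162 | 3.09 | 0.324 |
| 7 days | 43.2 | 0.0231 | 21.6 | 0.0463 |
| 30 days | 185.3 | 0.0054 | 92.6 | 0.0108 |

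From 1 hour to 30 days the rate changes by a factor of 30 × 24 = 720. That is the ratio of the two windows, so it shows only that a rate depends on its denominator. The one-hour row drives most of the spread.

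**What does not move.** The percentage of subjects with events is 1/188 = 0.53% or 1/94 = 1.06% under every window. The two counts do not move either.

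**Zero events.** The observed rate is then 0 under any window, and the observed percentage is also 0. Neither bare figure conveys precision, and either can be given an exact limit. For the percentage, the two-sided 95% upper limit is 1 − 0.025^(1/188) = 1.94%, or 1 − 0.025^(1/94) = 3.85%. For the rate, the exact Poisson limit is −ln(0.025) / patient-months = 3.689/185.3 = 0.020 per patient-month with 30 days in 188 subjects. The rate has no special defect here once its denominator is known.

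**Would another measure be better?** Events per subject is the planned number of events divided by the number of subjects, so it adds nothing to SAP 3.2. Events per limb examined has no place for a systemic event, or for an event in an enrolled subject before any BVE test. If observation time differs between subjects, for example because consent, BVE, duplex and ABPI fall on different days, person-time carries information that the other three summaries lack. The visible text does not rule this out.

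**Does a decision use the rate?** SAP 2.8 requires recruitment, measurement, valid data and the primary endpoint. SAP 2.3.1 defines that endpoint through accuracy against duplex. No safety threshold is visible anywhere.

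**The case for a change.** The best case for a change is that it would be cheap. One sentence could define the window or point to the CIP section that does, and nothing else in the study would be touched. The follow-up inconsistency does not depend on hidden text, since both statements stand in the same two-page summary, and sites have to apply the eligibility criteria.

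Part of this stands. The public text does not define patient-months, and N/A is hard to square with a follow-up period; the follow-up row and the two criteria should read consistently.

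What does not follow is that the plan lacks a definition. The available protocol is a summary, in which a reporting window would not normally appear. The SAP's numbering skips 2.2, 2.5 to 2.7, 2.10, 3.1 and 3.4, and its table of contents lists 3.6 and 4.0, which are absent from the text we have. Nor does the follow-up wording establish a fault in SAP 3.2: neither criterion mentions adverse-event observation or patient-months. With no visits planned, the phrases read most naturally as standard wording carried over from another protocol.

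**Conclusion.** No change to the plan is needed. The observation is accurate for the public text, but its reach is one of four descriptive adverse-event summaries. The other three remain fully interpretable, and the performance analysis and the success criteria do not use the rate. If the full CIP gives an adverse-event reporting window, the rate is defined. If it does not, a competent analyst would state the person-time used beside the rate, or note that it is not informative when observation ends at the test visit. In either case the safety conclusion would rest on the counts and percentages already planned. Replacing the rate with other measures would be a preference and would add no information.

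This rests on two assumptions: that no removed passage makes a decision depend on the monthly rate, and that the follow-up phrases in exclusion criteria 2 and 3 are drafting carry-over. The event count and windows in the table are illustrative and predict nothing about what the study will report.

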3.3 Subject Early Termination
There is no formal statistical rule for early termination of the clinical trial for insufficient effectiveness of the tested device defined.
the tested device defined.
3.5 Number of Subject Imbalance
All efforts will be made to maintain a balanced enrollment among the maximal 6 sites.

#### 5.0 ACRONYMS AND ABBREVIATIONS

Acronym or Abbreviation	Complete Phrase or Definition
ABPI	Ankle Brachial Pressure Index
AE	Adverse Event
BVE	BlueDop Vascular Expert
CI	Confidence Interval
CIP	Clinical Investigation Plan
CRF	Case Report Form
DBP	Diastolic Blood Pressure
FN	False Negative
FP	False Positive
ICF	Informed Consent Form
In/Ex	Inclusion/Exclusion
ITT	Intent-To-Treat population
PAD	Peripheral Arterial Disease
PP	per-protocol
SADE	Serious Adverse Device Effects
SAE	Serious Adverse Event
SAP	Statistical Analysis Plan
SOC	Standard Of Care
TN	True Negative
TP	True Positive
USADE	Unanticipated Serious Adverse Device Effects

_				
				_
_				

<del></del>

	I
 	

•

	1		

			, ,			
		_				$\blacksquare$
	 					$\Box$
		-				$\dashv$
						$\dashv$
						$\dashv$
						$\dashv$
						$\dashv$
				+		$\dashv$
						$\dashv$
_						
					_	
						$\neg$
				L		
						4
						-
						-
						1
						1
